11.9.2 Part B

Commercially Confidential Information

11.10 Power for analysis of key secondary variables

Not applicable

11.11 Interim analyses

12 Ethical considerations

12.1 Regulatory and ethical compliance

This clinical study was designed and shall be implemented, executed and reported in accordance with the ICH Harmonized Tripartite Guidelines for Good Clinical Practice, with applicable local regulations (including European Directive 2001/20/EC, US Code of Federal Regulations Title 21, and Japanese Ministry of Health, Labor, and Welfare), and with the ethical principles laid down in the Declaration of Helsinki.

12.2 Responsibilities of the investigator and IRB/IEC

Before initiating a trial, the investigator/institution must obtain approval/favorable opinion from the IRB/IEC for the trial protocol, written informed consent form, consent form updates, subject recruitment procedures (e.g. advertisements) and any other written information to be provided to subjects. Prior to study start, the investigator is required to sign a protocol signature page confirming his/her agreement to conduct the study in accordance with these documents and all of the instructions and procedures found in this protocol and to give access to all relevant data and records to Novartis monitors, auditors, Novartis Quality Assurance representatives, designated agents of Novartis, IRBs/IECs, and regulatory authorities as required. If an inspection of the clinical site is requested by a regulatory authority, the investigator must inform Novartis immediately that this request has been made.

For multi-center trials, a Coordinating Investigator will be selected by Novartis around the time of Last Patient Last Visit to be a reviewer and signatory for the clinical study report.

12.3 Publication of study protocol and results

The key design elements of this protocol will be posted in a publicly accessible database such as clinicaltrials.gov. In addition, upon study completion and finalization of the study report the results of this trial will be either submitted for publication and/or posted in a publicly accessible database of clinical trial results.

13 Protocol adherence

This protocol defines the study objectives, the study procedures and the data to be collected on study participants. Additional assessments required to ensure safety of subjects should be administered as deemed necessary on a case by case basis. Under no circumstances is an investigator allowed to collect additional data or conduct any additional procedures for any research related purpose involving any investigational drugs under the protocol.

Investigators ascertain they will apply due diligence to avoid protocol deviations. If an investigator feels a protocol deviation would improve the conduct of the study this must be considered a protocol amendment, and unless such an amendment is agreed upon by Novartis and approved by the IRB/IEC and health authorities, where required, it cannot be implemented.

ALT or AST elevation accompanied by symptoms Isolated ALT or AST elevation > 8 ×	 Hospitalize, if clinically appropriate Establish causality 	
ULN Jaundice	Complete CRFs per liver event guidance	
Isolated ALT or AST elevation > 5 to ≤ 8 × ULN	If confirmed, consider interruption or discontinuation of study drug	
	 If elevation persists for more than 2 weeks, discontinue the study drug 	
	Establish causality	
	Complete CRFs per liver event guidance	
Isolated ALT or AST elevation > 3 to ≤ 5 × ULN (patient is asymptomatic)	Monitor liver chemistry tests two or three times weekly	
Isolated ALP elevation	 Repeat liver chemistry tests within 48-72 hours 	
	 If elevation is confirmed, measure fractionated ALP; if >50% is of liver origin, establish hepatic causality 	
	Complete CRFs per liver event guidance	
Any AE potentially indicative of liver	Consider study treatment interruption or discontinuation	
toxicity	Hospitalize if clinically appropriate	
	Complete CRFs per liver event guidance	

Table 15-3 Exclusion of underlying liver disease

Disease	Assessment	
Hepatitis A, B, C, E	 IgM anti-HAV; HBSAg, IgM anti-HBc, HBV DNA; anti-HCV, HCV RNA, IgM & IgG anti-HEV, HEV RNA 	
CMV, HSV, EBV infection	 IgM & IgG anti-CMV, IgM & IgG anti-HSV; IgM & IgG anti- EBV 	
Autoimmune hepatitis	 ANA & ASMA titers, total IgM, IgG, IgE, IgA 	
Alcoholic hepatitis	 Ethanol history, gGT, MCV, CD-transferrin 	
Nonalcoholic steatohepatitis	Ultrasound or MRI	
Hypoxic/ischemic hepatopathy	 Medical history: acute or chronic CHF, hypotension, hypoxia, hepatic venous occlusion. Ultrasound or MRI. 	
Biliary tract disease	 Ultrasound or MRI, ERCP as appropriate. 	
Wilson disease	Caeruloplasmin	
Hemochromatosis	Ferritin, transferrin	
Alpha-1-antitrypsin deficiency	Alpha-1-antitrypsin	

16 Appendix 2: Specific Renal Alert Criteria and Actions

Table 16-1 Specific Renal Alert Criteria and Actions for Part A

Criteria	Action required
Serum creatinine (sCr) increase 25 – 49% compared to baseline	Consider causes and possible interventionsFollow up within 2-5 days
Serum creatinine increase ≥ 50% Protein-creatinine or albumin-creatinine ratio increase ≥ 2-fold	 Consider causes and possible interventions Repeat assessment within 24-48h if possible Consider drug interruption or discontinuation unless other causes are diagnosed and corrected Consider hospitalization and specialized treatment Consider causes and possible interventions
or new onset dipstick proteinuria ≥ 1+ or Albumin-creatinine ratio ≥ 30 mg/g or ≥ 3 mg/mmol; or Protein-creatinine ratio (PCR)≥ 150 mg/g or >15 mg/mmol	 Assess serum albumin & serum protein Repeat assessment to confirm Consider drug interruption or discontinuation unless other causes are diagnosed and corrected
New onset glucosuria on urine dipstick (unless related to concomitant treatment, diabetes)	Assess & document: Blood glucose (fasting) Serum creatinine Urine albumin-creatinine ratio
New hematuria on dipstick	 Assess & document: Urine sediment microscopy Assess sCr and urine albumin-creatinine ratio Exclude infection, trauma, bleeding from the distal urinary tract/bladder, menstruation Consider bleeding disorder

Additional specialized assessments are available to assess renal function or renal pathology. (Note: In exceptional cases when a nephrologist considers a renal biopsy, it is strongly recommended to make specimen slides available for evaluation by Novartis to potentially identify project-wide patterns of nephrotoxicity.)

Whenever a renal event is identified, a detailed subject history and examination are indicated to identify, document and potentially eliminate risk factors that may have initiated or contributed to the event:

- Blood pressure assessment (after 5 min rest, with an appropriate cuff size)
- Signs and symptoms such as fever, headache, shortness of breath, back or abdominal pain, dysuria, hematuria, dependent or periorbital edema
- Changes in blood pressure, body weight, fluid intake, voiding pattern, or urine output
- Concomitant events or procedures such as trauma, surgical procedures, cardiac or hepatic failure, contrast media or other known nephrotoxin administration, or other potential causes of renal dysfunction, e.g., dehydration, hemorrhage, tumor lysis

Table 16-2 Follow-up of renal events for Part A

Action	Follow up	
Assess*, document and record in the Case Report Form (CRF) or via electronic data load. Review and record possible contributing factors to the renal event (co-medications, other co-morbid conditions) and additional diagnostic procedures (MRI etc) in the CRF.	 Urine dipstick and sediment microscopy Blood pressure and body weight Serum creatinine, electrolytes (sodium, potassium, phosphate, calcium), bicarbonate and uric acid Urine output 	
Monitor subject regularly (frequency at	 Event resolution: (sCr within 10% of baseline or protein-creatinine ratio within 50% of baseline) 	
investigator's discretion) until:	 Event stabilization: sCr level with ±10% variability over last 6 months or protein- creatinine ratio stabilization at a new level with ±50% variability over last 6 months. 	

^{*} Urine osmolality: in the absence of diuretics or chronic kidney disease this can be a very sensitive metric for integrated kidney function that requires excellent tubular function. A high urinary osmolality in the setting of an increase in sCr will point toward a "pre-renal" cause rather than tubular toxicity.

Table 16-3 Specific Renal Alert Criteria and Actions for Part B

- положения поло	
Renal Event	Actions
Confirmed serum creatinine increase 25 – 49%	Consider causes and possible interventions Follow up within 2-5 days
Serum creatinine increase ≥ 50 % +	Consider causes and possible interventions Repeat assessment within 24-48h if possible Consider drug interruption or discontinuation unless other causes are diagnosed and corrected Consider patient hospitalization and specialized treatment
New onset dipstick proteinuria ≥ 3+ OR Protein-creatinine ratio (PCR) ≥ 1g/g Cr (or mg/mmol equivalent as converted by the measuring laboratory)	Consider causes and possible interventions Assess serum albumin & serum total protein Repeat assessment to confirm Consider drug interruption or discontinuation unless other causes are diagnosed and corrected
New onset hematuria ≥ 3+ on urine dipstick (excluding menstruation, infection, extreme exercise, or trauma)	Assess & document Repeat assessment to confirm Distinguish hemoglobinuria from hematuria Urine sediment microscopy Assess sCr Exclude infection, trauma, bleeding from the distal urinary tract/bladder, menstruation Consider bleeding disorder

^{*}Corresponds to KDIGO criteria for Acute Kidney Injury

Additional specialized assessments are available to assess renal function or renal pathology. (Note: In exceptional cases, when a nephrologist considers a renal biopsy, it is recommended to make slide specimen available for evaluation by the RSG to potentially identify project-wide patterns of nephrotoxicity.)

Whenever a renal event is identified, a detailed patient history and examination are indicated to identify and potentially eliminate risk factors that may have initiated or contributed to the event:

- Blood pressure assessment (after 5-minute rest, with an appropriate cuff size)
- Signs and symptoms like fever, headache, shortness of breath, back or abdominal pain, dysuria or hematuria, dependent or periorbital edema
- Changes in blood pressure, body weight, fluid intake, voiding pattern, or urine output
- Concomitant events or procedures such as trauma, surgical procedures, cardiac or hepatic failure, contrast media or other known nephrotoxin administration, or other diseases or causes, e.g., dehydration due to delirium, tumor lysis

Table 16-4 Renal Event Follow Up for Part B

FOLLOW-UP OF RENAL EVENTS

Assess, document and record in CRF

- Urine dipstick and sediment microscopy evidence of DIN: crystals, red blood cells (dysmorphic/glomerular vs. non-dysmorphic/non-glomerular), white blood cells, tubular epithelial cells
- · Blood pressure and body weight
- Serum creatinine, BUN, electrolytes (sodium, potassium, phosphate, calcium), bicarbonate and uric acid
- Urine output

Review and record possible contributing factors to the renal event (co-medications, other co-morbid conditions) and additional diagnostic procedures (MRI etc.) in the CRF

Monitor patient regularly (frequency at investigator's discretion) until -

- Event resolution: (sCr within 10% of baseline or PCR < 1 g/g Cr, or albumin-creatinine ratio <300 mg/g Cr) or
- Event stabilization: sCr level with ±10% variability over last 6 months or protein-creatinine ratio stabilization at a new level with ±50% variability over last 6 months.
- Analysis of urine markers in samples collected over the course of the DIN event

1.1 Scope of document

The RAP documents contain detailed information to aid the production of Statistics & Programming input into the Clinical Study Report (CSR) for trial “**CLNA043X2202**”.

The Statistical analysis plan (SAP) describes the implementation of the statistical analysis planned in the protocol.

1.2 Study reference documentation

Final study protocol amendment (v07) is available at the time of finalization of Statistical Analysis Plan.

1.3 Study objectives

1.3.1. Primary objective(s)

Primary objective(s)	Endpoints related to primary objectives

• To assess the efficacy of multiple i.a. injections of LNA043 in regenerating the articular cartilage tissue	
• Articular cartilage bi-layer collagen organisation evaluated with T2 relaxation times measured in superficial and deep layers by T2 mapping Magnetic Resonance Imaging (MRI) at Week 16 and 28 (Part A)• Change in cartilage volume and cartilage thickness in the index region at Week 28 and 52 (Part B)

• To assess safety and local tolerability of multiple i.a. injections of LNA043	
• Systemic and local Adverse Events• Electrocardiograms (ECGs)• Vital signs• Hematology, blood chemistry, urinalysis

1.3.2. Secondary objective(s)

Secondary objective(s)	Endpoints related to secondary objective(s)

• To assess the extent of the repair cartilage tissue following multiple i.a. injections of LNA043	
• Change in volume of cartilage defect filling evaluated with MRI at Week 16 and 28 (Part A)

	
• Articular cartilage bi-layer collagen organization evaluated with T2 relaxation times measured in superficial and deep layers by T2 mapping Magnetic Resonance Imaging (MRI) at Week 28 and 52 (Part B)• Serum and synovial fluid PK profile of LNA043 and ANGPTL3

• To evaluate systemic and local PK of LNA043 following multiple i.a. injections of LNA043• To assess the potential immunogenicity of LNA043	
• Presence and characterisation of anti-LNA043 antibodies in serum at Day 1, Day 15, Day 50, Day 106 and Day 190 (Part A) and Day 1, Day 29, Day 57, Day 85, Day 113, Day 197 and Day 365 (Part B)

Commercially Confidential Information

Commercially Confidential Information

1.4 Study design and treatment

This is a two-part non-confirmatory, randomized, placebo-controlled, patient and investigator blinded study, multiple doses in patients with a partial thickness cartilage lesion of the knee (Part A) and in patients with knee osteoarthritis (Part B). In total 135 patients are expected to be randomized into the study.

1.4.1 Part A

Approximately 60 patients with partial thickness cartilage lesion of the knee, with knee regions: defect tissue, weight bearing and non-weight bearing, will be enrolled in Part A and randomization will be stratified by type of lesion, either femoral condyle or patella. At least 48 patients are expected to complete the study (20% drop out rate). Additional patients may be enrolled if the dropout rate exceeds 20%. Participants will be treated at four treatment visits.

Patients will be assigned to one of the following “two (2)” treatment arms in a ratio of “3:1, A: B”.

Study treatments are defined as:

- A: single i.a. injection of 20mg (3mL) LNA043, once-weekly injections CCI
- B: single i.a. injection of placebo (3mL) to 20mg LNA043, once-weekly injections

Commercially Confidential Information

1.4.2 Part B

Approximately 75 patients will be enrolled in Part B and randomized. This is a non- confirmatory, randomized, placebo-controlled, patient and investigator blinded study in patients with Kellgren & Lawrence (K&L) with grade 2 or 3 with osteoarthritis (OA). At least 69 patients are expected to complete the study (10% drop out rate). Additional patients may be enrolled if the dropout rate will exceed 10%. Participants will be treated at four treatment visits.

Patients will be assigned to one of the following “three (3)” treatment arms in a ratio of “1:1:1, A:B:C”.

Study treatments are defined as:

A: single i.a. injection of 20 mg (4mL) LNA043, every 4 weeks	CCI
B: single i.a. injection of 40 mg (4mL) LNA043, every 4 weeks	CCI
C: single i.a. injection of placebo (4mL) every 4 weeks	CCI

Commercially Confidential Information

Commercially Confidential Information

2 First interpretable results (FIR)

Commercially Confidential Information

3 Interim analyses

Commercially Confidential Information

4 Statistical methods: Analysis sets

For subjects for which the actual treatment received does not match the randomized treatment the treatment actually received will be used for the analysis.

The safety analysis set will include all subjects that received any study drug.

The PK analysis set will include all subjects with at least one available valid (i.e. not flagged for exclusion) PK concentration measurement, who received any study drug and experienced no protocol deviations with relevant impact on PK data.

The pharmacodynamic (PD) analysis set will include all subjects with available PD data and no protocol deviations with relevant impact on PD data.

The analysis sets and protocol deviation codes are related as follows:

Table 4-1: Protocol deviation codes and analysis sets for Part A and Part B

Category Deviation code	Text description of deviation	Data exclusion
Subjects are excluded from PK analysis in case of these PDs:		
INCL01	Deviation from inclusion criterion 1	Yes
TRT01	Study treatment deviation, i.e. subject did not receive any study treatment or did not complete the full treatment (Part A) Major study treatment deviation i.e. subject did not receive the same dose throughout the study (Part B)	Yes
Subjects are excluded from PD analysis in case of these PDs:		
INCL01	Deviation from inclusion criterion 1	Yes
TRT01	Study treatment deviation, i.e. subject did not receive any study treatment or did not complete the full treatment (Part A) Major study treatment deviation i.e. subject did not receive the same dose throughout the study (Part B)	Yes

If updates to this table are needed, an amendment to the SAP needs to be implemented prior to DBL.

Additional analyses may be considered in relation to the quality and interpretability of the MRI assessments for cartilage volume and thickness. Flags (ANL0XFLs) based on the comments related to insufficient image quality (e.g., “low”) will be derived in order to define these sets. The derivation logic for these will be described in the Programming Data Specifications (PDS).

5 Statistical methods for Pharmacokinetic (PK) parameters

All subjects within the PK analysis set will be included in the PK data analysis.

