6.1.1 Investigational treatment and control drugs

Table 6-1 Overview of study medication

Study drug name	Formulation	Unit dose	Packaging	Provided by
LNA043	Lyophilisate in Vial (LYO)	10mg	Open label bulk supply	Novartis
Placebo to LNA043	Lyophilisate in Vial (LYO)	0mg	Open label bulk supply	Novartis

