8.6.6 Pregnancy and assessment of fertility

All pre-menopausal women who are not surgically sterilized will have pregnancy testing. See the Assessment Schedule, Table 8-1 and Table 8-2, for timing of the protocol required pregnancy testing; additional pregnancy testing may be performed to meet local requirements*. A positive urine pregnancy test requires immediate interruption of study treatment until serum β-hCG is performed and found to be negative.

*If additional pregnancy testing is needed per local requirements, those additional results will be kept as source documentation only.

8.6.7 **Immunogenicity**

IG samples will be collected at the time points defined in the Assessment schedule (Section 8.1 and Section 8.2).

Further details on sample collection, numbering, processing and shipment can be found in the SOM

Immunogenicity analytical method 8.6.7.1

A validated ligand binding assay will be used for the detection of anti-LNA043 antibodies, and cross-reactivity to ANGPTL3 and ANGPTL4. Positive samples will be further analyzed for presence of neutralizing antibodies using a validated ligand binding assay.

IG samples remaining after immunogenicity analysis may be used for exploratory assessment or other bioanalytical purposes (e.g. cross check between different sites). Given the exploratory nature of the work, the analytical method used for those assessments will not be validated.

8.7 **Pharmacokinetics**

Validated bioanalytical assays will be used to determine LNA043 and ANGPTL3 in synovial fluid and serum.

PK samples will be collected at the timepoints defined in the Assessment schedule, Table 8-1 and Table 8-2. Follow instructions outlined in the SOM regarding sample collection, numbering, processing and shipment. See Section 8.9 regarding the potential use of residual samples.

In order to better define the PK profile, the timing of the PK sample collection may be altered based on emergent data. The number of samples/blood draws and total blood volume collected will not exceed those stated in the protocol.

PK samples will be obtained from all subjects.

Commercially Confidential Information

For standard pharmacokinetic abbreviations and definitions see the list provided at the beginning of this protocol.

Due to a limited PK sampling, only summary statistics of measured PK concentrations will be reported, and no further PK parameters will be determined in this study.

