11.1 **Analysis sets**

For all analysis sets, subjects will be analyzed according to the study treatment(s) received.

The safety analysis set will include all subjects that received any study drug.

The PK analysis set will include all subjects with at least one available valid (i.e. not flagged for exclusion) PK concentration measurement, who received LNA043 and with no protocol deviations that impact on PK data.

The primary pharmacodynamic (PD) analysis set will include all subjects with available PD data. The secondary PD analysis set will include all subjects with available PD data and no protocol deviations with relevant impact on PD data. Details of which protocol deviations have impact on PD data will be provided in the Statistical Analysis Plan (SAP).

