5.1 Descriptive analyses

Due to a limited PK sampling, only summary statistics of measured PK concentrations will be reported, and no further PK parameters will be determined for this study.

LNA043 and ANGPTL3 serum and synovial fluid concentration data will be listed by subject, and visit/sampling time point, separately for each study part. Descriptive summary statistics will be provided by treatment, study part and visit/sampling time point, including

Commercially Confidential Information

Summary statistics will include mean (arithmetic and geometric), Standard Deviation (SD), CV (arithmetic and geometric), median, minimum and maximum.

The PK analysis will be done separately for part A and part B.

6 Statistical methods for Pharmacodynamic (PD) parameters

All subjects within the PD analysis set will be included in the efficacy PD data analysis, unless otherwise stated. For MRI related assessments, all subjects within the PD analysis set and subjects who completed Week 28 and/or Week 52, for Part B will be included.

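### SAP Table 4-1 removes whole subjects from the PK analysis for a treatment deviation, although concentrations taken before the deviation remain valid and PK is only summarised visit by visit

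*SAP*

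**What the plan says.** SAP section 4 admits to the PK set any subject with at least one valid concentration "who received any study drug and experienced no protocol deviations with relevant impact on PK data". Table 4-1 then puts this into operation under the line "Subjects are excluded from PK analysis in case of these PDs". Apart from a consent deviation (INCL01), the only code listed is TRT01:

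- **Part A:** the "subject did not receive any study treatment or did not complete the full treatment (Part A").
- **Part B:** a major treatment deviation, defined as not having had the same dose throughout the study. A missed or stopped injection is not named.

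Nothing in the table keeps samples collected before the deviation. SAP section 5 bases the PK analysis on this set. SAP 5.1 says that, because sampling is limited, "only summary statistics of measured PK concentrations will be reported", by treatment, study part and visit. The secondary endpoint is "Serum and synovial fluid PK profile of LNA043 and ANGPTL3".

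Protocol 11.1 defines the set differently, limiting it to subjects "who received LNA043 and with no protocol deviations that impact on PK data". Protocol 8.7 states "PK samples will be obtained from all subjects".

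**The concern.** An exclusion for a treatment deviation makes sense when the quantity analysed depends on the whole dosing course, such as an accumulation ratio or a steady-state exposure. Nothing of that kind is derived here. Each summary is a cross-section at one visit, so a deviation at injection 4 is irrelevant to the table for injection 1. A subject-level rule still removes that subject from every visit, in serum and synovial fluid, for both analytes.

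The loss may also be informative. The protocol contains routes by which treatment stops early while the patient may stay in the study: prohibited medication in Part A (section 5.2), certain liver events (Appendix 1) and pregnancy (section 9.6). TRT01 makes no exception for stops that the protocol itself calls for. If such patients differ in exposure, the PK tables describe a selected group, and the people whose early exposure may be of interest are absent from them.

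**Working it through.** The documents give no count of subjects excluded from PK, so there is no stated figure to reproduce. The check sets the rules side by side and then gives a scale.

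**1. The rules compared**

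| Place | Unit or criterion |
|---|---|
| SAP section 4, set definition | One valid concentration is enough to enter; only deviations with relevant PK impact exclude |
| SAP Table 4-1, TRT01 | Whole subject excluded |
| SAP 5.1 | Concentrations summarised per visit; no further PK parameters |
| Protocol 11.5 | Subjects with PK concentrations missing in some but not all periods are kept in a mixed model |

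The first, third and fourth rows work at the level of the sample or visit. Only Table 4-1 works at the level of the subject. The never-treated clause of TRT01 adds nothing for PK, because the set already requires receipt of study drug. The operative clause in Part A is therefore non-completion.

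**2. One patient**

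Both parts have four treatment visits (SAP 1.4.1, 1.4.2). A Part A patient who has injections 1 to 3 and misses the fourth has 3 of 4 dosing visits unaffected; Table 4-1 uses 0 of 4. A Part B patient given a different dose at the fourth visit likewise loses three unaffected cycles. A Part B patient who simply stops after three injections of the same dose may or may not be excluded: the wording does not settle it.

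**3. Illustrative scale, Part A LNA043 arm**

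- Inputs: 60 patients, 3:1 allocation, 20% dropout, 48 completers (SAP 1.4.1). Check: 60 × 0.80 = 48.
- LNA043 patients: 60 × 3/4 = 45.
- Assumption, deliberately at the high end: all dropout falls in the dosing phase, so 45 × 0.20 = 9 stop early and 36 complete. The 20% is dropout from the study, not non-completion of treatment.
- Unit: the sampling schedule is not in the available text, so I count dosing-visit occasions. Completers contribute 36 × 4 = 144.
- If the 9 stop after k injections, they hold 9k valid occasions that Table 4-1 removes. The share recovered by the fix is 9k / (144 + 9k).

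| k | Valid occasions removed | Total if kept | Share |
|---|---|---|---|
| 1 | 9 | 153 | 5.9% |
| 2 | 18 | 162 | 11.1% |
| 3 | 27 | 171 | 15.8% |

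At the first injection, the table would rest on 36 patients rather than 45. If nobody stops early, the effect is zero.

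**4. Evidence on frequency**

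Protocol Table 1-1 (cut-off 31 January 2020) shows no adverse events leading to discontinuation of treatment among 43 + 15 = 58 Part A patients. It does not count stops for other reasons.

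**5. Placebo patients**

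Planned placebo patients number 60/4 = 15 in Part A and 75/3 = 25 in Part B, so 40 of 135 (29.6%). They fall outside the set under Protocol 11.1. Under SAP section 4 they are inside it, since Protocol Table 6-1 lists "Placebo to LNA043" as a study drug.

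**The case against.** The best defence is that little depends on this. The study is non-confirmatory, PK is secondary and descriptive, and no decision rule visible in the documents uses it. Dose adjustment is not permitted (Protocol 6.6) and site staff give every injection (Protocol 6.8), so misdosing should be rare. A Part B patient who has had two dose levels has no clean treatment group afterwards, so some exclusion is right. Table 4-1 can still be amended before database lock.

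Most of that stands, and it limits the importance of the point. It does not justify the rule: the mixed-dose argument applies only to samples after the change.

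Three stronger readings are tempting, and the documents do not support them.

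- **That the analysis has no placebo reference for endogenous ANGPTL3.** This follows only from the Protocol 11.1 wording. The SAP set admits placebo patients, and SAP 5.1 summarises ANGPTL3 by treatment. What remains is a mismatch between the documents.
- **That no change from baseline is planned for ANGPTL3.** The sentence in SAP 5.1 that lists the summaries is cut by redaction, as is the matching text in Protocol 11.7.2, and the sampling schedule is not available. Absence cannot be inferred.
- **That patients who stop because of a reaction vanish from the PK tables.** Part A shows no such stop at the cut-off, and the Part B trigger is a change of dose, which does not clearly include stopping.

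**Conclusion.** The point holds as a narrow one. For PK, TRT01 excludes whole subjects where only the samples after the deviation are affected, and this goes beyond the SAP's own relevance criterion. It is clearest for Part A non-completers. In Part B it applies to a changed dose and is ambiguous for a missed or stopped injection.

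The size is unknown and probably small in Part A: zero with no early stops, and up to 15.8% of LNA043 dosing-visit occasions under the high-end assumption that all 20% dropout occurs during dosing, after the third injection. The conclusion assumes that the redacted text contains no exception for samples before the deviation and no PK parameter spanning several doses; the visible text of SAP 5.1 rules out the latter. This is a cheap improvement to a descriptive secondary output. It does not threaten the trial's conclusions.

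The difference between Protocol 11.1 and SAP section 4 over placebo patients is a minor matter of alignment.

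**What to change.** 1. In the PK block of SAP Table 4-1, replace the subject-level TRT01 exclusion with a sample-level one. Keep every valid concentration up to the deviation, including any pre-dose sample at the visit where it occurs. Flag later concentrations as excluded from the summaries but still list them. The existing provision for flagging individual concentrations can carry this.
2. State whether a missed or stopped injection in Part B counts as TRT01 for PK, so that the two parts can be programmed without interpretation.
3. Reconcile Protocol 11.1 with SAP section 4 so that placebo patients stay in the PK set for ANGPTL3, as the SAP already provides; a line in the SAP recording the departure from the protocol would do.

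The cost is a table edit, one derived flag and a SAP amendment, which section 4 requires before database lock. No new samples are needed. The downside is that patient numbers will differ slightly between visits, so each PK table should show its n by visit. The change concerns PK only; the TRT01 entry for the PD set is a separate question.
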